7.4. Ethics and Informed Consent

Permission to conduct this study will be requested from institutional or national review boards according to local legislation. Informed consent will be waived since this is a retrospective study and only anonymised data will be collected.

7.5. Schedule

Only TAAD patients undergoing open heart surgery between 1 January 2010 and 31 December 2024 will be retrospectively retrieved and enrolled in the study. Deadline for submission of data is set up for 31 December 2021.

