3. SYNOPSIS

Title of Study	Transatlantic Registry of Type A Aortic Dissection (TARTAAD)		
Sponsor	University Hospital of Helsinki (Finland)		
Study	Primary Hypothesis: understanding the patient's conditions and		
Hypothesis	treatment strategies which are associated with postoperative		
	outcomes is essential for an appropriate management of acute TAAD		
Study	Primary objective: to identify the predictors influencing early and late mortality		
Objectives	in TAAD patients undergoing open heart surgery		
	• Secondary objectives: to elucidate and identify predictors of: 1) re-		
	exploration for bleeding; 2) cerebrovascular accident 3) surgical site infection;		
	4) blood transfusion; 5) acute kidney injury; 6) length of intensive care unit		
	(ICU) stay; 7) length of hospital stay and 8)		
	reoperation after hospital discharge; 8) late survival; 9) rate of late re-intervention.		
Study Design	Retrospective observational cohort study registry		
Planned Sample	This study will use data from 32 high-volume aortic centers.		
Size	It is anticipated that the final database will approximately contain clinical		
Culain at	details for more than 10000 patients.		
Subject	Inclusion criteria:		
Selection Criteria	• Type A aortic dissection or intramural hematoma involving the aortic		
Criteria	root/ascending aorta; • Patients aged > 18 years: • Symptoms started within 7 days from surgery; • Primary surgical repair of acute type A aortic dissection;		
	Any other major cardiac surgical procedure		
	concomitant with surgery for type A aortic dissection		
Intervention	This is a non-interventional study		
Study period	1 January 2010 – 31 December 2024		
Follow-up/End-	31 December 2025		
study			
Primary	Mortality rate during the index hospital stay until last follow-up control		
Outcomes	Cumulative incidence of reoperation on the aorta during the index hospital		
	stay until last follow-up control (any surgical and endovascular procedure on		
	any segment of the aorta for aortic dissection or its		
0	related complication)		
Secondary	1) Incidence of stroke; 2) Incidence of acute kidney injury; 3) Incidence of		
Outcomes	surgical site infection; 4) Incidence of reoperation for bleeding; 5) Incidence		
	and amount of blood transfusion; 6) Length of stay in the intensive care unit; 7) Incidence of global brain ischemia; 8) Incidence of paraplegia/paraparesis; 8)		
	late survival; 9) rate of late re-intervention		
	late salvival, syrate of late to intervention		

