8.1. Number of Participants

An estimated number of 20-25 patients affected by TAAD and undergoing open heart surgery are usually admitted in mid/high-volume aortic centres (1). Therefore, it is estimated that the registry will encompass more than 5000 patients in total. Locally, the number of patients admitted to Glenfield Hospital (University Hospitals of Leicester NHS Trust) fulfilling the inclusion criteria between 1 January 2010 and 31 December 2025 is (average) 15-20 per year.

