8.4. Frequency of Analysis

Statistical analyses and sub-group study analyses will be performed after the end of recruitment data (31 December 2025).

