12.5. End of the study

The study will be concluded with the end of patient recruitment: 31-Dec-2025. This will represent also the end of follow-up and data collection.

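### Section 7.5 closes data submission three years before its own surgery window ends, and the protocol leaves unclear whether 2025 surgery is eligible

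*Protocol*

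**What the plan says.** The protocol gives dates for the cohort, the follow-up and the data in five places.

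- **Synopsis (section 3).** The study period is "1 January 2010 – 31 December 2024". Follow-up and the study end on "31 December 2025".
- **Section 7.5.** The surgery window is set by this sentence: "Only TAAD patients undergoing open heart surgery between 1 January 2010 and 31 December 2024 will be retrospectively retrieved and enrolled in the study". The next sentence is "Deadline for submission of data is set up for 31 December 2021".
- **Section 8.1, Number of Participants.** The count of eligible patients at the Leicester site "between 1 January 2010 and 31 December 2025 is (average) 15-20 per year".
- **Section 8.4, Frequency of Analysis.** Analyses follow "after the end of recruitment data (31 December 2025").
- **Section 12.5.** The closing date is given as follows: "The study will be concluded with the end of patient recruitment: 31-Dec-2025. This will represent also the end of follow-up and data collection".

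The amendment history table is empty, so nothing marks any of these dates as superseded.

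**The concern.** Two separate conflicts appear.

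First, the two sentences of section 7.5 cannot both be followed, because data on surgery in 2022 to 2024 cannot be submitted by the end of 2021. Section 12.5 gives a different close of data collection.

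Second, the end of the eligible surgery window is 2024 in the synopsis and section 7.5, but section 8.1 counts eligible patients to the end of 2025. Sections 8.4 and 12.5 can be read the same way.

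These dates bear on the primary outcomes. Mortality and aortic reoperation both run to the last follow-up contact with no fixed horizon, so the cut-off decides how much observation time each patient contributes. Section 7.7 defines loss to follow-up relative to the date of data collection, so an unclear collection date also changes who counts as lost. Section 13.2 states an aim of outcomes beyond 10 years, which depends directly on the cut-off. Centres retrieve their own records, so unclear dates could be applied differently from one centre to another.

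**Working it through.** The plan states no figure for this point that could be reproduced. The check is calendar arithmetic on its dates.

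**Dates side by side**

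| Section | Last eligible surgery | End of follow-up | End of data submission or collection |
|---|---|---|---|
| 3, Synopsis | 31 Dec 2024 | 31 Dec 2025 | not given |
| 7.5 | 31 Dec 2024 | not given | 31 Dec 2021 |
| 8.1 | 31 Dec 2025 (site count) | not given | not given |
| 8.4 | 31 Dec 2025, if recruitment means surgery | not given | not given |
| 12.5 | 31 Dec 2025, if recruitment means surgery | 31 Dec 2025 | 31 Dec 2025 |

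The follow-up cut-off agrees wherever it is given. The submission or collection date and the last eligible surgery date do not.

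**Surgery after the 2021 deadline**

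- From 31 December 2021 to 31 December 2024 is 1096 days, or 3 years.
- The window from 1 January 2010 to 31 December 2024 is 15 years. The share after the deadline is 3/15 = 20%.
- With a window to the end of 2025 the share would be 4/16 = 25%.

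**Patients, assuming even accrual over 15 years**

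- With the synopsis total of 10000: 0.20 × 10000 = 2000 lost, 8000 left.
- With the section 8.1 total of 5000: 0.20 × 5000 = 1000 lost, 4000 left.
- Both remainders reach the 4000 that section 8.2 calls enough. (The protocol states both totals as lower bounds.)

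**At least 10 years of potential follow-up, assuming even accrual**

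- Cut-off 31 December 2025: surgery in 2010 to 2015 qualifies, 6/15 = 40% of the intended cohort.
- Cut-off 31 December 2021: surgery in 2010 and 2011 qualifies, 2/15 = 13% of the intended cohort, or 2/12 = 17% of those operated on by the end of 2021.
- The difference between the two cut-offs is 4 years of follow-up.

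**If 2025 surgery is eligible**

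- The minimum potential follow-up falls from 365 days (31 December 2024 to 31 December 2025) to 0 days.
- At even accrual, 1/16 = 6.25% of patients would have less than one year of potential follow-up.

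**Site count in section 8.1, at 15 to 20 patients per year**

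- To 2021: 12 × 15 = 180 to 12 × 20 = 240.
- To 2024: 15 × 15 = 225 to 15 × 20 = 300.
- To 2025: 16 × 15 = 240 to 16 × 20 = 320.

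**The case against.** The strongest reply is that the intended dates can largely be recovered. The synopsis and section 7.5 agree on the surgery window, and the synopsis and section 12.5 agree on the follow-up cut-off. The 2021 deadline looks like a date carried over from the ERTAAD registry, a name still used in sections 5.1, 7.1 and 13.4. A centre that noticed an impossible deadline would more likely query it than discard three years of patients that the preceding sentence tells it to enrol. This stands, and it is why the losses above are not forecasts.

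A reader might also infer that the protocol ends recruitment in both 2024 and 2025. The text does not go that far. No section says that recruitment ends in 2024: the synopsis and section 7.5 set a surgery window. In a retrospective registry, recruitment in sections 8.4 and 12.5 can mean the end of record retrieval. Section 8.1 does not fit that reading, since it counts eligible patients to the end of 2025, but it is a volume estimate for one hospital and not an eligibility rule. The right description is that the eligibility of 2025 surgery is unclear.

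A third tempting inference is that unequal follow-up would distort the comparison of centres. The between-centre analysis in section 8.3 is limited to early outcomes by logistic regression, so length of late follow-up does not enter it. Calendar era could, but only if centres actually applied different windows. Short potential follow-up for the most recent patients is ordinary administrative censoring in a survival analysis and is not itself a bias.

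None of this removes the contradiction inside section 7.5 or the disagreement between section 8.1 and the stated surgery window.

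**Conclusion.** The protocol is wrong as written on two points. The only submission deadline it gives is impossible for 3 of the 15 eligible years and conflicts with the end of data collection in section 12.5. It also leaves unclear whether surgery in 2025 is eligible. The follow-up cut-off of 31 December 2025 is itself consistent.

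The loss of about 20% of the cohort, and the fall from about 40% to 13% with at least 10 years of potential follow-up, hold only if the 2021 deadline is enforced and accrual is even over the window. They bound the harm and do not predict it. A reader might infer that the study would fall short of its required size, but the documents do not support this: even after a 20% loss, either stated total still reaches the 4000 patients named in section 8.2. What is at stake is cohort membership and observation time for the primary outcomes. These should not depend on which section a centre happens to read.

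**What to change.** Use one set of dates throughout, following the synopsis: index surgery from 1 January 2010 to 31 December 2024, and follow-up cut-off 31 December 2025.

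- **Section 7.5:** delete the 2021 deadline and give one submission or data-lock date on or after the follow-up cut-off.
- **Section 8.1:** change the end of the site's window to 31 December 2024. The date itself has to change, because the sentence counts eligible patients.
- **Section 8.4:** call 31 December 2025 the end of follow-up, not of recruitment.
- **Section 12.5:** do the same, reword so that the two sentences do not merely repeat each other, and align the end of data collection with the new submission date. Otherwise a submission date after 31 December 2025 would again conflict with this section.

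The cost is protocol wording, the amendment approvals that sections 12.1 and 12.2 already describe, and a notice to centres. No analysis method and no sample size figure in section 8.2 depends on the change.

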7.6. Source of Data

Source documents are original documents, data, and records at Glenfield Hospital (University Hospitals of Leicester NHS Trust). These include hospital records, clinical and office charts, laboratory and pharmacy records, and imaging test results. No hospital documents will be stored or retained.

7.7. Variables to be Collected and Definitions

Variables to be collected are defined according to relevant literature and definition provided below:

Onset of symptoms to surgery

It refers to the time (in hours) between the onset of symptoms associated with TAAD and the start of surgery.

Estimated distance to hospital

Distance (in km) between the place where patients experience onset of symptoms associated with TAAD and the hospital where primary surgery was performed.

Nighttime surgery

It refers to a procedure which started between 20:00-08:00.

Preoperative laboratory parameters

Data on preoperative levels of creatinine (in micromol/L), hemoglobin (in g/L), platelet count (x10/L) and arterial lactate (in mmol/L) as measured immediately before the start of surgery.

Preoperative parameters of myocardial ischemia

Coronary malperfusion will be defined according to preoperative increased levels of troponin/CK-MB and/or ECG changes of myocardial ischemia. When cardiac biomarkers are measured, this information will be gathered.

Renal function

Baseline renal function will be classified according to the estimated glomerular filtration rate (eGFR) calculated using the Chronic Kidney Disease Epidemiology Collaboration (CKD-EPI) equation (9) and the European Kidney Function Consortium (EKFC) equation (10). The severity of renal failure will be classified in different stages as listed in Table 1.

Table 1. Stages of chronic kidney disease.

Stages	eGFR (mL/min/1.73 m ²)
1	≥90
2	60-89
3	45-59
4	30-44
5	15-29
6	<15 or dialysis

Abbreviation: eGFR, estimated glomerular filtration rate.

Genetic syndromes

Genetic syndromes may lead to aortopathies and TAAD (11). Information on any specific genetic syndrome associated with TAAD will be collected in this registry.

Family history of aortic dissection and aneurysm

It refers to dissection and/or aneurysm involving any segment of the aorta in first or second-degree relatives.

Prior aortic surgery

Any open surgery or endovascular repair on any segment of the aorta. Details on the type of procedure will be collected.

latrogenic TAAD

TAAD secondary to any surgical or endovascular procedure performed within a week before surgery. Details on the timing and type of procedure will be collected.

Preoperative antithrombotic drugs

Exposure to any of the following antithrombotic drugs within 2 days from surgery: aspirin, clopidogrel, ticagrelor, prasugrel, ticlopidine, low-molecular weight heparin, unfractionated heparin, fondaparinux, direct oral anticoagulants and/or warfarin. When data on preoperative antithrombotic drugs were not available, this will be reported in the datasheet.

Arterial hypertension

Systemic arterial pressure > 150/80 mmHg or use of antihypertensive drugs.

Diabetes

Hyperglycemia requiring treatment with insulin or oral drugs.

Prior stroke

Any preoperative focal or global neurological syndrome caused by ischemia or hemorrhage not resolving within 24 h. It refers to a neurological event occurring any time, but excluding those acute neurological events related to TAAD.

Prior transient ischemic attack

Any preoperative focal or global neurological syndrome caused by ischemia or hemorrhage resolving within 24 h. It refers to a neurological event occurring any time, but excluding those acute neurological events related to TAAD.

Pulmonary disease

Use of bronchodilators and/or steroids for lung diseases (12).

Extracardiac arteriopathy

One or more of the following: lower limb claudication, critical limb ischemia, carotid occlusion or >50 % stenosis, major amputation for arterial disease, previous or planned intervention on the abdominal aorta or on the extremities or carotid arteries (12).

Prior myocardial infarction

History of myocardial infarction excluding to those events (coronary malperfusion) related to TAAD.

Prior percutaneous coronary intervention

History of percutaneous coronary intervention any time before surgery excluding those procedures resulting in iatrogenic TAAD.

Critical preoperative state

Critical preoperative state will be defined as one of the following conditions: 1) preoperative external cardiac massage any time before surgery, 2) cardiogenic shock requiring inotropes any time before surgery, 3) preoperative invasive mechanical ventilation before admission to the anesthetic/operating room and 4) preoperative acute renal failure (anuria or oliguria <10ml/hr) (12). Data on each of these conditions will be collected.

Urgency of the procedure

Urgency of the procedure will be classified in five categories whose definition criteria are summarized in Table 2.

Table 2. Urgency of the procedure.

Urgency	Definition		
Urgent	Scheduled procedure performed in a patient with stable conditions during the index hospitalization		
Emergency grade 1	Emergency procedure performed in a patient with stable conditions before the beginning of the next working day after decision to operate		
Emergency grade 2	Emergency procedure performed for hemodynamic instability requiring inotropes before the beginning of the next working day after decision to operate – no cardiopulmonary resuscitation with external cardiac massage		
Salvage grade 1	Salvage procedure: patients requiring cardiopulmonary resuscitation with cardiac massage between induction of anesthesia and initiation of cardiopulmonary bypass		
Salvage grade 2	Salvage procedure: patients requiring cardiopulmonary resuscitation with external cardiac massage en route to the operating theatre or prior to induction of anesthesia		

Penn Classification

The Penn Class of each patient will be derived considering the components of this risk classification (15).

Neurological status immediately before procedure

Data on derangements of neurological status such as unconsciousness before sedation, hemiplegia/hemiparesis, paraplegia/paraparesis, dysarthria/aphasia, vision disturbances, visuospatial neglect (individual fails to detect stimuli on a space that is contralateral to a hemispheric lesion), severe confusion, or intubated/sedated at arrival will be reported as separate variables.

Malperfusion

Malperfusion refers to acute organ ischemia secondary to aortic branch vessel hypoperfusion. This severe condition is usually classified based on clinical signs and symptoms (15,16). Herein, myocardial malperfusion will be defined as any changes in ST level in electrocardiogram and/or an increase in cardiac enzymes. Cerebral malperfusion will be defined as signs and symptoms related to acute preoperative stroke or cerebral hypoperfusion. Spinal malperfusion will be defined as acute paraparesis/paraplegia. Mesenteric malperfusion will be as sudden, mild-to-severe abdominal pain with or without nausea and vomiting, which is accompanied by rectal bleeding or bloody diarrhea in case of colon ischemia (17). Renal malperfusion will be defined as anuria/oliguria. Peripheral malperfusion will be defined as loss of pulse with or without sensory or motor deficits of any limb.

Preoperative computed tomography findings

Preoperative computed tomography scans will be reviewed for evaluation of the extent of aortic dissection/intramural hematoma in different segments of the aorta and its branches. Dissection of the aortic branches will be defined as any intimal flap at the origin of the artery causing stenosis of any severity. This applies also to aortic branches perfused through the false lumen.

Data on maximal diameter of the aortic root, ascending aorta, aortic arch, descending aorta and abdominal aorta will be collected.

Intramural hematoma

Intramural hematoma is defined as a contained aortic wall hematoma within the media, but without intimal flap formation. Patients with intramural hematoma and concomitant intimal flap in any segment of the aorta will be classified as having typical aortic dissection.

Heart valve status and left ventricular function

Data from preoperative echocardiographic evaluation of the aortic valve, mitral valve and left ventricular function will be collected.

Arterial and venous cannulation sites

It refers to the primary cannulation sites. Any switch to other cannulation site before initiation of cardioplegia will be described.

Intraoperative findings

Data on the intraoperative findings of the pericardium, ascending aorta and aortic arch will be collected. The extent of aortic dissection at the level of the Valsalva sinuses and morphology of the aortic valve will be described. Injury of the coronary ostia will be classified as spontaneous when related only to dissection or iatrogenic when related to the procedure. Injury of the coronary ostia can be both spontaneous and iatrogenic.

Surgical repair

Data on the type of aortic root/ascending aorta and aortic arch surgical repair will be collected along with data on any major concomitant cardiac surgery procedure. Details of the level of aortic anastomosis and suture techniques will be documented.

Cardiopulmonary bypass parameters

Data on duration of myocardial ischemia, cardiopulmonary bypass, hypothermic circulatory arrest and retrograde or antegrade cerebral perfusion will be collected. When multiple periods of perfusion or organ ischemia have occurred, the total length of these periods will be reported. The lowest temperature during hypothermic circulatory arrest will be documented. Hypothermic circulatory arrest will be defined as the duration of discontinuation of systemic perfusion independently of the use and duration of antegrade or retrograde cerebral perfusion. Many colleagues may not agree with this definition criterion. However, this definition may be helpful from a statistical point of view to identify different perfusion strategies. The use and duration of antegrade or retrograde cerebral perfusion will be of help to further identify different strategies used at each participating center.

- Outcomes and Their Definition Criteria
- Intraoperative death

Death occurred in the operating room at the end of the index procedure.

Hospital death

All-cause death having occurred during the index hospitalization, i.e., at the institution where surgery for TAAD was performed.

Stroke

Acute episode of a focal or global neurological deficit with at least one of the following: change in the

level of consciousness, hemiplegia, hemiparesis, numbness, or sensory loss affecting one side of the body, dysphasia or aphasia, hemianopia, amaurosis fugax, or other neurological signs or symptoms consistent with stroke duration of a focal or global neurological deficit ≥ 24 h; OR <24 h if available neuroimaging documents a new brain hemorrhage or infarct; OR the neurological deficit results in death (17). Stroke will be classified as ischemic, hemorrhagic or both.

Global brain ischemia

Diffuse hypoxic damage as diagnosed at brain imaging and electroencephalography.

Paraplegia/paraparesis

Bilateral weakness and/or multimodality sensory disturbance below the level of the ischemic spinal lesion.

Mesenteric ischemia

Abdominal pain with or without nausea and vomiting and rectal bleeding or bloody diarrhea (18). Diagnosis is made at imaging, endoscopy and/or surgery.

Sepsis

Sepsis is defined as severe systemic infection diagnosed in blood cultures, which may lead to life-threatening organ dysfunction.

Deep sternal wound infection/mediastinitis

Proven infection involving deep sternal wound tissues and/or mediastinum.

Acute Heart failure

Acute heart failure requiring prolonged postoperative treatment with inotropes (>24 hours) and/or mechanical circulatory support.

Mechanical circulatory support

The use of intra-aortic balloon pump (IABP) and/or venoarterial extracorporeal membrane oxygenation (VA-ECMO) for postoperative acute heart failure unresponsive to medical treatment. The configuration and duration of treatment of these salvage therapies will be documented.

Postoperative peak level of creatinine, dialysis and acute kidney injury

It will be defined according to postoperative change in serum creatinine levels and its severity will be stratified according to the Kidney Disease: Improving Global Outcomes (KDIGO) criteria (19) (Tab.

3). However, in view of the prolonged hospital treatment of TAAD patients, changes in serum

creatinine level will be evaluated as occurring during the index hospitalization. We recognize that acute kidney injury can also be diagnosed according to urine output measure, however, this method is not feasible in retrospectively gathered data and this will not be considered in the present study. Dialysis will be defined as temporary when discontinued and permanent if continued at the time of discharge from the institution where the index surgery was performed.

Table 3. Definition criteria of postoperative acute kidney injury.*

Stages	Serum creatinine
1	1.5-1.9 times baseline OR
1	≥0.3 mg/dL (≥26.5 micromol/L) increase
2	2-2.9 times baseline
3	≥3.0 times baseline OR Increase to ≥4 mg/dL (≥353.6 micromol/L) OR Initiation of renal replacement therapy

^{*}Changes in serum creatinine level occurring during the index hospitalization.

Perioperative bleeding

Data on the number of transfused units of red blood cell will be collected. The E-CABG bleeding classification has been proposed as a simple classification of perioperative bleeding (20) and it has been shown to be comparable to the Universal Definition of Perioperative Bleeding (21) in predicting early mortality (22). Herein we will adopt a simplified version of the E-CABG perioperative classification, which defines severe bleeding as reoperation for excessive intrathoracic bleeding and/or transfusion of more than 4 units of red blood cells (Table 4). The number of transfused units of red blood cells will be considered as the overall number of transfused units during the index hospitalization (both during the stay in the intensive care unit and in the ward).

Table 4. Simplified E-CABG perioperative bleeding classification (20).

Grades	Intervention for treatment of bleeding
0	No RBC transfusion or transfusion of 1 unit of RBCs
1	Transfusion of 2-4 units of RBCs
2	Transfusion of 5-10 units of RBCs
3	Transfusion of >10 units of RBCs

Abbreviation: RBC, red blood cell.

Reoperation for bleeding

Chest reopening for excessive bleeding. It qualifies as a reoperation for bleeding also any reoperation for hemostasis in patients in whom the sternum was left open. Chest reopening for hemodynamic instability without excessive bleeding, pericardial/pleural puncture or chest drain insertion for retained blood syndrome do not qualify as reoperation for bleeding.

Postoperative lowest level of hemoglobin

The lowest level of hemoglobin will be recorded as a further measure of perioperative bleeding.

Laryngeal nerve palsy

Injury of the recurrent laryngeal nerve injuries resulting in vocal cord paresis and in voice changes or hoarseness.

Tracheostomy

Tracheostomy performed any time during the index hospitalization.

Procedures for vascular complications

Any vascular and endovascular procedure for ischemic or bleeding complications.

These complications will encompass neurologic complications, mesenteric ischemia, upper and lower limb ischemia as well as bleeding from the aorta and its branches.

Length of stay in the intensive care unit

Overall length of treatment in the intensive care unit, including readmissions, at the institution where the primary surgery for TAAD was performed, i.e. during the index hospitalization.

Last follow-up date

It refers to the last date when the patient was reportedly alive or the date of her/his death.

Patients lost to follow-up

Patient will be considered lost to follow-up when no information is available on her/his survival status within the last 3 months of the date of data collection.

Reoperation data

Data on any surgical and/or endovascular reoperation on any segment of the aorta and/or aortic valve will be collected. Information on the aortic segments treated during reoperation/s will be collected along with the indication for repeated aortic procedure.

Noteworthy, aortic reoperation will be classified as a prophylactic procedure when it was performed for completion of the primary procedure for aortic remodeling without evidence of TAAD-related complications.

8. Statistical Analysis

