6.2. Objectives

The primary objective of this retrospective study is to identify the predictors influencing the mortality rate during the index hospital stay until last follow-up control, and the cumulative incidence of reoperation on the aorta during the index hospital stay until last follow-up control. Secondary objectives include: 1) incidence of stroke; 2) incidence of acute kidney injury; 3) incidence of surgical site infection; 4) incidence of reoperation for bleeding; 5) incidence and amount of blood transfusion; 6) length of stay in the intensive care unit; 7) incidence of global brain ischemia; 8) incidence of paraplegia/paraparesis

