13. FUTURE DEVELOPMENT

13.1. Implications for the Treatment of TAAD Patients

Analysis of the data from this collaborative registry will allow analysis of contemporary results of a large number of TAAD patients with a lengthy follow-up period. We expect that the multicentre nature of this registry will allow reduction in the risk of bias related to institutional volume and surgical experience. In fact, all the participating centers have an annually rate of at least 25 procedures for acute TAAD and have an aortic surgery program which would facilitate an adequate follow-up and management of possible late aortic events after primary repair of TAAD. Therefore, we expect to gather data which will provide important insights into the assessment of the operative risk of patients with acute TAAD and conclusive results on the value of different surgical and perfusion strategies for this emergency condition.

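### Follow-up and loss to follow-up are defined by survival status alone, so the primary reoperation outcome has no end date of its own and its incidence may be understated

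*Protocol*

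**What the plan says.** The Synopsis and section 6.2 (Objectives) of the protocol name two primary outcomes: mortality, and "the cumulative incidence of reoperation on the aorta during the index hospital stay until last follow-up control". The term *last follow-up control* is not defined anywhere in the protocol.

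Section 7.7 (Variables to be Collected and Definitions) has three relevant entries:

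- The end of follow-up is a single date, defined thus: "It refers to the last date when the patient was reportedly alive or the date of her/his death".
- Loss is judged in the same way. Someone counts as lost "when no information is available on her/his survival status within the last 3 months of the date of data collection".
- On repeat aortic procedures, the protocol undertakes the following: "Data on any surgical and/or endovascular reoperation on any segment of the aorta and/or aortic valve will be collected". The entry adds the segments treated and the indication. It lists no date up to which reoperation status is known.

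Section 7.6 (Source of Data) describes source documents in text that names a single hospital: "These include hospital records, clinical and office charts, laboratory and pharmacy records, and imaging test results". Section 13.1 says that participating centres "have an aortic surgery program which would facilitate an adequate follow-up and management of possible late aortic events". Patients were operated on between 1 January 2010 and 31 December 2024 (section 7.5), and follow-up ends on 31 December 2025 (section 12.5). Potential follow-up is therefore about 1 to 16 years.

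**The concern.** A survival date is the right end of follow-up for mortality. It is right for reoperation only if whatever showed the patient to be alive would also have shown a reoperation. Section 7.7 does not require that. A report that the patient is alive is enough to set the date and to satisfy the 3-month rule. For patients who die, the date is the date of death, however long before it they were last seen. If the last follow-up date is used for reoperation, a patient with no recorded reoperation counts as reoperation-free up to that date.

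Time that nobody observed then enters the denominator with no chance of contributing an event, which pulls the cumulative incidence down. The pull grows with follow-up, and long-term durability beyond 10 years is a stated aim (sections 13.2 and 13.3).

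The more serious risk is a difference between groups. Section 8.2 makes total arch repair against more limited resection a main research topic, with late reoperation as the endpoint. Section 8.3 (Statistical Analysis) itself says that centre results may depend on referral pathway. If reoperation is ascertained for longer in one centre or after one type of repair, an apparent difference can arise without a true one. Propensity matching on baseline variables does not correct unequal outcome ascertainment.

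**Working it through.** No figure in the protocol rests on this definition, so there is none to reproduce. The check illustrates how large the effect could be.

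**Inputs**

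- Reoperation hazard h, from section 8.2: the planning value is 95% freedom from distal reoperation. It is read here at 8 years, the time point of the cited 95.3%. h = −ln(0.95)/8 = 0.00641 per year.
- Death hazard m = 0.03 per year. **Assumption**; not in the protocol.
- Rate l at which reoperation ascertainment ends while vital status stays known: 0, 0.05, 0.10 or 0.20 per year. **Assumption**; the protocol states no gap.

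**Formulae**

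True cumulative incidence with death competing:

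CIF(T) = h/(h+m) × [1 − exp(−(h+m)T)]

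A reoperation is recorded only if it occurs before death and before ascertainment ends. If everyone is followed to the last-alive date, the reported value is

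CIF_rep(T) = h/(h+m+l) × [1 − exp(−(h+m+l)T)]

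**Results at T = 8 years**

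| l per year | h/(h+m+l) | 1 − exp(…) | Reported | Relative understatement |
|---|---|---|---|---|
| 0 | 0.1761 | 0.2527 | 4.4% | 0% |
| 0.05 | 0.0742 | 0.4991 | 3.7% | 17% |
| 0.10 | 0.0470 | 0.6642 | 3.1% | 30% |
| 0.20 | 0.0271 | 0.8491 | 2.3% | 48% |

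At 10 years the reported values are 5.4%, 4.3%, 3.5% and about 2.4% to 2.5%.

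**Simulation.** A cohort of 400,000 with uniform entry over 15 years and administrative end at year 16, analysed with the Aalen-Johansen estimator, gave 4.42%, 3.66%, 3.09% and 2.28% at 8 years when censored at the last-alive date. Censoring at the date ascertainment ended gave 4.42%, 4.40%, 4.42% and 4.42%. It recovers the truth because loss of contact was simulated as unrelated to reoperation risk.

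**Sensitivity**

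- A death hazard of 0.02 or 0.05 instead of 0.03 gives 16% to 17%, 29% to 30% and 47% to 49% for the three non-zero rates.
- A milder gap, l = 0.02, gives 7% at 8 years.
- A fixed gap without deaths (true value 5.0% at 8 years): if status stops at 4 years in 30% of patients, the result is 0.7 × 5.00 + 0.3 × 2.53 = 4.3%. If it stops at 4 years in all, 2.5%.

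**Differential ascertainment.** Give two strategies the same true hazard, with ascertainment ending at 5% per year in one and 15% in the other. At 8 years the reported values are 3.7% and 0.00641/0.18641 × 0.7749 = 2.7%, a ratio of about 0.72. This is a ratio of incidences and only roughly comparable with the hazard ratio of 0.73 in section 8.2. Neither loss rate comes from the protocol.

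**The case against.** A reader might infer that patients certainly stay at risk long after a reoperation could have been recorded, and that the reported incidence is therefore too low. The documents do not support this, for five reasons.

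- **No gap is stated.** The protocol describes no death register or other vital-status source reaching further than hospital records. If the last-alive date comes from the same contact that would reveal a reoperation, the gap and the bias are small or nil.
- **The outcome's end point is ambiguous.** *Last follow-up control* could mean a clinic visit. On that reading the outcome already ends at the last clinical contact.
- **No censoring rule for reoperation is written down.** One may stand in a statistical analysis plan that is not shown.
- **Reoperations elsewhere are not excluded.** Section 7.7 asks for any reoperation. Where the protocol means the index institution only, as for hospital death and intensive care stay, it says so.
- **The data form is not shown.** The Access datasheet (section 8.5) and the database attachment (section 9.2) may hold a suitable date.

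All five stand, and they make the bias conditional. They do not supply the missing definition. The only follow-up date and the only loss rule that the protocol defines ignore reoperation status, and the outcome's own end point is undefined. The possible analysis plan does not settle the matter either, because it cannot censor at a date that was never collected. The statement in section 13.1 about aortic programmes gives neither a date nor a measure of completeness.

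**Conclusion.** The point holds in conditional form. The protocol ties the end of follow-up and loss to follow-up to survival alone and leaves the end point of a primary reoperation outcome undefined. If the last-alive date is used for that outcome, the cumulative incidence is understated wherever vital status is known for longer than reoperation status, and comparisons are biased if that gap differs between centres or strategies.

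The relative understatement at 8 years runs from zero with no gap to about 17%, 30% and 48% at assumed ascertainment-loss rates of 5%, 10% and 20% per year. These figures rest on the planning rate read at 8 years, constant hazards and an assumed death hazard of 3% per year; the last matters little. The loss rates drive the result, and nothing in the protocol informs them. Whether a gap exists in this registry cannot be judged from the protocol. The remedy is cheap enough to justify without proof that it does.

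**What to change.** 1. Define *last follow-up control* for reoperation as the last date on which aortic reoperation status was known, from a clinical visit, aortic imaging, documented contact with the patient or treating hospital, or a register check. Record that date for every patient, unless the data form already holds it.
2. Censor the reoperation analysis at that date, with death before it as the competing event. Keep the last-alive date for mortality.
3. Apply the loss-to-follow-up rule separately to survival and to reoperation. Report completeness of both by centre and repair strategy.
4. As a sensitivity bound, also report reoperation censored at the last-alive date.

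The cost is one more field to abstract, shorter reoperation follow-up and wider intervals. There is also a statistical downside. Censoring at last contact assumes that loss of contact is unrelated to reoperation risk. If well patients stop attending while those with complications return, it can overstate the incidence. Step 4 is there for that reason: the two analyses err in opposite directions under these two failures, and the distance between them shows how much the result depends on incomplete ascertainment.
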